8.5 Medications

Updates to current medications or any new or changed medications are requested at each evaluation. Medications because of intervention related to the study treatment are documented and will be correlated with reported adverse events.

8.6 Adverse Events

Participants are queried about any side effects or adverse experiences related to the Vivaer procedure that they may have experienced. Incidence (type, severity, relatedness) of adverse events overall and by follow-up interval were recorded according to definitions provided in the study protocol.

9 STATISTICAL ANALYSIS**9.1 Analysis Populations****Full Analysis Set (FAS):**

The FAS is comprised of all enrolled participants that underwent the study procedure and met eligibility criteria.

Per-Protocol Eligible Set (PPS):

The PPS is comprised of all participants who met enrollment eligibility criteria, underwent the study and no major protocol deviations.

Safety Analysis Set:

The safety analysis population is comprised of all enrolled participants that have received any study-specific procedure, including screening procedures (eg, nasal endoscopy) and any part of the Vivaer procedure, including anesthesia.

9.2 General Considerations and Statistical Methods

Summary descriptive statistics, including mean, median, standard deviation, minimum, maximum, and interquartile range for continuous measures, and frequencies and percentages for categorical outcomes will be presented for all variables of interest. Outcome measures will be presented by time. Confidence intervals will be included for means and medians where appropriate for the various outcome measures.

Informational and exploratory outcomes analyses will use $P < .05$ as a measure of statistical significance. Where feasible, longitudinal analyses of individual outcome

Statistical Analysis Plan TP900 (AERWAY)

measures will incorporate *P*-value adjustment for comparisons of multiple time points. No adjustments will be made due to analyzing multiple outcome measures.

Analyses using repeated measures linear mixed models with multiple comparisons of time points are anticipated for outcome measures conventionally considered continuous data (NOSE). Components of the NOSE Scale score have also been treated as continuous but may also be analyzed using generalized linear models as outcomes represented by ordered categories.

Results will be presented using least square (adjusted) means where data are not complete across all time points.

Nonparametric analysis will be employed where gross violations of assumptions for parametric analyses are demonstrated.

Correlation analysis and regression modeling may be employed for exploratory analyses of relationships between and among various participant demographic and history characteristics and outcome measures, particularly NOSE Scale scores and components.

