An ongoing follow up study after the prospective, nonrandomized, multicenter 26-week (pivotal) trial was performed to continue to follow subjects for 2 years after the primary treatment. The objective of the study was to evaluate the long-term durability of benefits associated with the treatment procedure using the Vivaer[®] ARC Stylus for nasal airway obstruction. The Nasal Obstruction Symptoms Evaluation (NOSE) survey and a Quality of Life survey developed by Aerin Medical were administered at 12, 18, and 24 months after the subjects treatment procedure to subjects who agreed to participate and provided informed consent for the long-term data collection. Subjects completed the NOSE and Aerin Medical Quality of Life surveys in person with a study representative, by telephone, or by mail-in response.

Of the original 50 patients in the pivotal trial, 49 were eligible to participate in the long-term follow-up study and 39 enrolled in the study. Subjects from all original pivotal study sites were enrolled.

The mean NOSE score at baseline was 80.8 (SD 10.7) for subjects participating in this study. All subjects had nasal obstruction at baseline categorized as either severe (46%) or extreme (54%). The mean NOSE score for subjects in this study had significantly improved ($p < 0.001$) to 24.9 (SD 21.3) at the 26-week endpoint of the pivotal study with a mean change from baseline of 55.9 (SD 23.6). Significant improvement ($p < 0.001$) in mean NOSE score was maintained through the 12-, 18-, and 24-month evaluations (27.5, 32.7, and 26.5, respectively). At 26 weeks, severe and extreme nasal obstruction rates had decreased from 100% to 10% (4 of 39) of subjects, and at 12-, 18-, and 24-months, 17%, 26% and 17% of subjects had severe or extreme nasal obstruction, respectively.

Using the definition of responder of at least a 15-point improvement in NOSE score, 92% of subjects participating in this study were classified as responders at 26 weeks and at 12 months 94% were classified as responders (3 subjects were not evaluated at 12 months). There were 3 participating subjects classified as non-responders at 26 weeks who met responder status at 12 months and 2 subjects classified as responders at 26 weeks who became non-responders at 12 months. All 39 subjects were evaluated at 18 months with a responder rate of 87% and at 24 months 36 of 39 subjects were evaluated and had a responder rate of 97%.

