2 INTRODUCTION

The purpose of this statistical analysis plan (SAP) is to prespecify statistical analysis methods for supporting completion of publications and clinical study report (CSR) of TP900 (AERWAY) for the Vivaer product.

The AERWAY postmarket study was primarily designed to generate additional effectiveness evaluations through observational reporting of outcomes measures defined in the protocol. No specific hypotheses or hypothesis tests were defined in the study protocol. This SAP outlines the data summaries, statistical techniques, and analyses that will be used to evaluate the effectiveness and safety measures and to propose subgroup analyses of interest.

Results of analyses performed under this SAP may be included in regulatory submissions, clinical study reports and/or manuscripts. Additional exploratory analyses, which are not defined in this SAP, may be performed to further support the clinical development program. Those additional analyses will be detailed in an amendment to this plan and/or documented in the CSR.

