8.2 NOSE Scale Score

To evaluate the significance of a patient's nasal obstruction both before and after the procedure, this study used the well-known patient-reported NOSE Scale for determining the primary assessment of treatment effectiveness. The NOSE Scale is a validated disease-specific health status instrument used by clinicians to measure the outcome of patients treated for nasal obstruction.¹ The NOSE Scale consists of 5 items, each scored using a 5-point Likert scale to make a total score range of 0 through 100, where higher scores indicate worse obstruction. Severity of symptoms can be classified as mild (range, 5-25), moderate (range, 30-50), severe (range, 55-

Statistical Analysis Plan TP900 (AERWAY)

75), or extreme (range, 80-100) nasal obstruction, based on responses to the NOSE survey.²

Treatment responder based on NOSE Scale improvement

Individual participant success (responder) is defined as at least 1 NOSE Scale class improvement, (eg, going from a score in the severe range (55-75) at baseline to a score in the moderate range (30-50) at the follow-up evaluation), or an improvement (decrease) in NOSE Scale score of 20% or more from baseline to the follow-up time point. Other levels of success (definitions of responder) may also be explored.

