9.7 Demographics and Baseline Characteristics

Demography and baseline characteristics will be summarized using frequencies and percentages for categorical factors and mean, standard deviation, minimum and maximum, median, and interquartile range for continuous factors.

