9.8 Outcome Measures Analyses

Data collected at postprocedure evaluation time points conducted after a participant received additional ENT procedures outside of the study protocol will be excluded

Statistical Analysis Plan TP900 (AERWAY)

from analysis of efficacy outcomes measures as these additional procedures would likely confound the effect of the original Vivaer treatment. For example, a participant who received a septoplasty after the 12-month evaluation will have any efficacy outcome measures that were collected after the septoplasty (24 months and 36 months) excluded from the analysis. Results after receiving additional treatments may be summarized separately.

Nasal Assessment - The visual physical and endoscopic assessment factors summarized to include frequency and percentage of responses in each category for each component of the nasal assessment at baseline, just prior to procedure, immediately after procedure, and 3 months after the procedure.

NOSE Scale score - Categorical responses and scores on the NOSE Scale and its individual components will be subject to multiple summary methods and analyses including the:

- Mean and mean change from baseline at the 3-, 6-, 12-, 24-, and 36-month follow-up evaluations.
- Distribution of NOSE Scale score severity categories (mild, moderate, severe, extreme) at the 3-, 6-, 12-, 24-, and 36-month follow-up evaluations displayed as number and percent.
- Mean, change from baseline in mean, and response distribution of the 5 components of the NOSE Scale score (nasal congestion, nasal blockage, trouble breathing, trouble sleeping, and getting enough air during exercise) at the 3-, 6-, 12-, 24-, and 36-month follow-up evaluations.
- Proportion (%) of responders based on improvement in NOSE Scale score at the 3-, 6-, 12-, 24-, and 36-month follow-up evaluations be displayed as number and percent.

VAS for pain - Summary will include mean (median) VAS pain scores assessed postprocedure and at 3 months.

Participant QoL Questionnaire – Responses to questionnaire items will be summarized by response category (frequency and percent) and by mean (median) response where appropriate at the 3-, 6-, 12-, 24-, and 36-month follow-up evaluations.

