9.9 Subgroup and Other Analyses and Summaries

Several subgroups of interest have been identified for further exploration in relation to the effect on NOSE Scale scores and responder proportions:

- valve collapse mechanism (dynamic, static, mixture)
- prior septoplasty or turbinate surgery
- presence/absence of septal deviation
- presence/absence of enlarged turbinates.

Other areas of interest include:

- Characteristics of treatment nonresponders.
- Substudy of endoscopic nasal assessment images of participants identified with septal deviation. The study will examine the feasibility of grading the degree of septal deviation and assess the potential for correlation with NOSE Scale scores.

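### Does the SAP need to name a baseline-adjusted contrast for its exploratory NOSE subgroup comparisons?

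*SAP*

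**What the plan says.** Section 9.2 of the SAP gives the general approach to continuous outcomes: "Analyses using repeated measures linear mixed models with multiple comparisons of time points are anticipated for outcome measures conventionally considered continuous data (NOSE"). It does not say whether baseline is one of the time points, and it names neither a baseline NOSE covariate nor a subgroup term. The adjusted (least squares) means mentioned there are tied to incomplete data, not to baseline severity. The same section adds that "regression modeling may be employed for exploratory analyses of relationships between and among various participant demographic and history characteristics and outcome measures", and sets P<.05 for exploratory work.

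Section 9.9 says: "Several subgroups of interest have been identified for further exploration in relation to the effect on NOSE Scale scores and responder proportions". The factors are valve collapse mechanism, prior septoplasty or turbinate surgery, septal deviation, and enlarged turbinates. No model or contrast is given.

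Section 9.8 lists both the level and the change: "Mean and mean change from baseline at the 3-, 6-, 12-, 24-, and 36-month follow-up evaluations". In section 8.2 a responder improves by at least one severity class or shows "an improvement (decrease) in NOSE Scale score of 20% or more from baseline to the follow-up time point". Section 9.7 describes baseline summaries ("Demography and baseline characteristics will be summarized using frequencies and percentages for categorical factors") without naming a breakdown by subgroup. Section 2 records that "No specific hypotheses or hypothesis tests were defined in the study protocol".

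**The concern.** A subgroup that starts with worse NOSE scores has more room to improve, and part of its worse start may be regression to the mean. If follow-up scores hardly depend on baseline, comparing subgroups on change turns nearly all of a baseline gap into apparent extra benefit. A subgroup that merely started worse could then be described as responding better. Comparing follow-up scores could give the opposite impression. The SAP permits both and does not say which it will report.

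Section 5 of the SAP says the larger sample was meant to support subgroup work, and section 2 allows results to go into manuscripts and regulatory submissions. The responder rule also depends on baseline. From 75 the smallest qualifying drop is 15 points (20% of 75; the next class down would need 25). From 80 it is 5 points, because 75 is already a lower class.

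**Working it through.** **Inputs.** Protocol section 5.0, long-term follow-up study, n = 39: baseline 80.8 (SD 10.7), 26-week score 24.9 (SD 21.3), "with a mean change from baseline of 55.9 (SD 23.6"). Pivotal trial, n = 49 analysed: 26-week SD 20.4, mean change 54.8 (SD 21.9), lower 95% bound 49.6. SAP section 3: 125 planned. Assumed, because the documents do not give them: a 62/63 split, a 5-point baseline gap, two-sided tests, one visit.

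**The documents' own figures.** 80.8 − 24.9 = 55.9, as stated. For the pivotal bound, 54.8 − 1.677 × 21.9/√49 = 49.55, which matches 49.6 as a one-sided bound.

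**How much of a baseline gap reaches the change score.**
- r = (10.7² + 21.3² − 23.6²)/(2 × 10.7 × 21.3) = (114.49 + 453.69 − 556.96)/455.82 = 0.025
- Slope of improvement on baseline = 1 − r × 21.3/10.7 = 0.951
- SE = 21.3 × √[(1 − r²) × 38/37]/(10.7 × √38) = 0.327. With t(37) = 2.026 the 95% CI is 0.29 to 1.61.

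The pivotal baseline SD is printed as 0.8. That would give r = (0.64 + 416.16 − 479.61)/32.64 = −1.92, which is impossible, so it cannot be used. Borrowing 10.7 gives a slope of 0.78. This is not independent support, since the 39 subjects come from the same trial.

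**If the truth is no difference at equal baseline.** Expected change contrast = 5 × 0.951 = 4.76. SE = 23.6 × √(1/62 + 1/63) = 4.22. Noncentral t gives 20% rejection (6% to 47% over the slope CI).

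**If the truth is equal mean improvement.** The change contrast has expectation 0. The baseline-adjusted contrast has expectation −4.76. Residual SD = 21.3 × √(1 − r²) = 21.29, and SE = 21.29 × √[1/62 + 1/63 + 5²/(123 × 10.7²)] = 3.91. Noncentral t gives 23% rejection.

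**Simulation** (20,000 runs per row, normal scores, residual SD 21.3, 62/63 split):

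| Truth | Slope | Gap | Change | Follow-up | Baseline-adjusted |
|---|---|---|---|---|---|
| No difference at equal baseline | 0.95 | 5 | 20% | 5% | 5% |
| Equal improvement | 0.95 | 5 | 5% | 26% | 23% |
| No difference at equal baseline | 0.78 | 5 | 16% | 6% | 5% |
| Equal improvement | 0.78 | 5 | 5% | 25% | 17% |
| Both (no gap) | 0.95 | 0 | 5% | 5% | 5% |

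The adjusted contrast holds its 5% level in the first and third rows because those rows are its own null hypothesis. Under the other null it fails about as often as change does under the first.

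**Responder proportions.** Take mean baselines of 78 and 83, baseline SD of about 10.4 to 10.8 within 60 to 100, follow-up SD 21.3 and slope 0.95. The modelled gap is then 1.2 percentage points at a follow-up mean of 24.9 and 2.2 at 32.7 (0.2 to 4.7 over the slope CI). A wider pair, 75 and 85, gives 2.5 and 4.6 (0.4 to 9.7).

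**The case for a change.** The best argument for a change is that a SAP exists to fix such choices before results are seen. Here two permitted contrasts can disagree, P<.05 will be applied, and the sample was partly justified by these subgroups. One covariate and one table would cost almost nothing, and analysing follow-up score given baseline is a familiar default.

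Part of this stands. The text does leave the contrast open, and a sentence naming it would be good practice.

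The argument for making the adjusted model the lead analysis does not stand. In a randomised comparison the groups share a baseline distribution in expectation, so change and adjusted analyses estimate the same effect and adjustment gains precision. These subgroups are defined by anatomy and surgical history, and a baseline difference may be part of what distinguishes them. Which subgroup improved more, and which ends better from the same start, are then separate questions. The SAP has no hypothesis that ranks one above the other.

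The risk of a misleading report is also limited. If mean and mean change are both shown by subgroup, as section 9.8 lists them overall, the baseline mean can be recovered, apart from subjects missing at a visit. Section 9.2 leaves room for regression on history characteristics. Section 2 requires analyses not defined in the SAP to be recorded in an amendment or the clinical study report. Adjustment over visits, where feasible, lowers the error rate too: at a Bonferroni level of .01 for five visits, the 20% falls to about 7%.

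**Conclusion.** The omission is real but calls for no change. It is unspecified detail in an exploratory section, joined to a choice between two legitimate questions. For the assumed 5-point gap (nearly half a baseline SD), the change contrast rejects about 20% of the time when the truth is no difference at equal baseline. The adjusted contrast rejects about 23% of the time when the truth is equal improvement. With no systematic gap all three reject at about 5%, and the documents show no gap.

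The 0.95 carry-over comes from 39 earlier subjects at a single 26-week visit. Its interval (0.29 to 1.61) does not establish that most of a gap would carry over, and no SDs are given for this study's own visits. The responder effect is small for a 5-point gap. The overall single-arm change from baseline is unaffected throughout.

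An analyst can meet the concern when reporting by showing baseline NOSE beside follow-up and change for each subgroup, and by saying which question any P value answers.

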9.3 Data Pooling

All study data will be pooled across study sites.

9.4 Missing Values

Outcome measures will be analyzed by using available data only. No imputations are anticipated unless part of a subgroup analysis of interest.

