9.5 PHASE 5: STUDY EXIT

Subjects will be determined exited from the study when they complete the questionnaires for each required follow up or are determined as exited if a circumstance removes them for a specific reason earlier than planned. Subjects meeting the study requirements as planned will be exited from the study after the 36 month follow-up data collection. If a subject reaches the 36 month follow-up point and is experiencing new or ongoing adverse event, the study sponsor and treating investigator should be contacted to discuss the need and/or methods for continued surveillance of the event.

Subjects that completed the 24-month follow-up and exited per protocol version D will be invited to continue participation in the study through their 36 month post Vivaer procedure date. Subjects who elect to continue with the study will be asked to re-consent for their participation through 36 months. Subjects that decline 36-month follow-up participation or re-consent, will be exited from the study after their 24 month follow-up data collection. Reasons for declining participation in the 36 month extension will be recorded in the eCRF.

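### The responder and severe/extreme percentages, above all at 36 months, drop re-treated participants and those who declined the extension, and no supportive analysis is planned

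*SAP*

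**What the plan says.** Three rules together decide who is counted.

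- **Missing values (SAP 9.4).** "Outcome measures will be analyzed by using available data only. No imputations are anticipated unless part of a subgroup analysis of interest".
- **Further procedures (SAP 9.8).** Efficacy values recorded after an ENT procedure outside the protocol are dropped. In the SAP's example, a participant who has a septoplasty after month 12 "will have any efficacy outcome measures that were collected after the septoplasty (24 months and 36 months) excluded from the analysis". The only provision for those values is permissive: "Results after receiving additional treatments may be summarized separately".
- **The extension (Protocol 9.5).** "Subjects that completed the 24-month follow-up and exited per protocol version D will be invited to continue participation in the study". Continuing requires a new consent, and "Subjects that decline 36-month follow-up participation or re-consent, will be exited from the study after their 24 month follow-up data collection". The protocol adds: "Reasons for declining participation in the 36 month extension will be recorded in the eCRF".

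SAP 9.8 gives the severity distribution and the responder proportion as counts and percentages at every visit. The responder item ends "36-month follow-up evaluations be displayed as number and percent". SAP 9.2 anticipates a repeated-measures mixed model with least-squares means for NOSE as a continuous score, and foresees confidence intervals for means and medians.

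SAP 8.4 says that part four of the QoL questionnaire asks about additional nasal surgery. SAP 9.8 summarises QoL items at each follow-up visit.

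**The concern.** SAP section 3 gives the purpose as collecting longer-term effectiveness data up to 36 months, so the course of the responder and severe/extreme percentages from 3 to 36 months will be read as evidence of durability. Under the three rules, a change or lack of change in that course may partly reflect who is still counted.

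The further-procedure rule matters most. A participant who seeks another procedure for persisting obstruction is plausibly someone in whom the treatment did not last. The plan takes that person out of both numerator and denominator.

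No hypothesis is tested, so no success decision is at risk. SAP section 2 does allow the results into manuscripts and regulatory submissions, where a single 36-month percentage may be quoted without its selection.

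**Working it through.** **1. What the plan provides for these percentages.** The model in SAP 9.2 applies to the continuous score, and the generalized linear models mentioned there apply to the NOSE components. The FAS and PPS in SAP 9.1 differ by protocol deviations, not by missing data. SAP 9.9 lists subgroups and the characteristics of nonresponders, but no comparison of participants with and without 36-month data. The SAP contains no sensitivity analysis for missing values or for the further-procedure exclusion.

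**2. Figures available.** The documents give no retention, re-procedure rate or expected 36-month rate for this study, so there is no figure of its own to reproduce. Protocol 5.0 gives figures for the earlier follow-up study. That study used a 15-point responder rule, which is not the rule in SAP 8.2, so it serves as illustration only.

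**3. Reproducing the earlier study.** At 24 months, 36 of 39 were evaluated.
- Responders, reported as 97%: 35/36 = 97.2%, the only count out of 36 that rounds to 97%.
- Severe or extreme, reported as 17%: 6/36 = 16.7%. No count out of 39 rounds to 17% (6/39 = 15.4%, 7/39 = 17.9%), so the denominator was those evaluated.

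**4. Bounds over the 39 enrolled there**, with x events among n observed and N in total: lower = x/N, upper = (x + N − n)/N.
- Responders: 35/39 = 89.7% to 38/39 = 97.4%.
- Severe or extreme: 6/39 = 15.4% to 9/39 = 23.1%.

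These are limits, not estimates.

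**5. Effect of the further-procedure rule in this study.** At one visit let n be observed, k excluded after a procedure, and e = k/(n + k).
- Responder rate p with the excluded counted as failures: pn/(n + k) = p(1 − e), a drop of p × e. At an assumed p = 90%:
  - e = 2%: 90.0% becomes 88.2% (−1.8 points)
  - e = 5%: 85.5% (−4.5)
  - e = 10%: 81.0% (−9.0)
- Severe/extreme rate s becomes (sn + k)/(n + k) = s + e(1 − s). Taking s = 17% from the earlier study as an assumption, the rise is 0.02 × 83 = 1.7, 0.05 × 83 = 4.2 or 0.10 × 83 = 8.3 points.

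**6. The denominator of e.** The share is over observed plus excluded participants, not over the FAS. If 10% of the FAS is excluded and 20% is otherwise missing, e = 10/(70 + 10) = 12.5%, and the drop at 90% is 0.90 × 12.5 = 11.25 points, not 9.0.

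**The case against.** The exclusion is open and reasoned: SAP 9.8 argues that a later procedure would confound the effect of the study treatment. That is a sound reason not to use the later score. It is not a reason to leave the event out of every summary of durability, and counting the event as non-response uses no confounded score.

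The study is descriptive, counts shown with percentages let a reader recover each denominator, and SAP section 2 permits further analyses. All true. They would then be chosen after the 36-month results are visible, and a recovered denominator does not say why people are missing.

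The mixed model for mean NOSE uses all retained visits and gives a partial check under missing at random. That stands for the mean, although post-procedure values are excluded there too.

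A reader might infer that the plan reports nothing on further surgery. It does: the QoL summary should yield a related count at each visit. That count is not the number excluded from the efficacy percentages. Nasal surgery is narrower than ENT procedures, and only those who return the questionnaire are counted.

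A reader might also infer that the 36-month percentages are inflated. The documents do not show this. In the earlier study, 49 − 3 = 46 participants were 26-week responders. Of the 39 who joined the follow-up, 92% is 36. Assuming the same 49 participants, 46 − 36 = 10 responders remain among the 49 − 39 = 10 who did not join. That opt-in step does not suggest favourable selection.

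**Conclusion.** The concern holds as a gap in planned supportive analysis. The percentages describe a selected group, the further-procedure rule can only remove people from them, and nothing planned shows how much this matters.

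The direction and size of any bias in this study are unknown. The drops of 1.8 to 9.0 points rest on an assumed 90% rate and an assumed excluded share of 2% to 10% of observed plus excluded participants. The earlier study's bounds come from another cohort and another responder rule, so they neither measure nor predict the effect here. The change should be made, but no pass/fail conclusion turns on it.

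**What to change.** Amend SAP 9.4 and 9.8.

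1. **Disposition at each visit.** Report the FAS number, the number with data, and the numbers (a) excluded after an additional ENT procedure, (b) declined the extension or exited at 24 months under version D, and (c) otherwise missing. Put each participant in one category and state the order of precedence.
2. **Main and supportive summaries.** Keep the observed-case proportions as the main summary and add exact 95% confidence intervals. Add one supportive analysis in which participants excluded because of an additional procedure for nasal obstruction count as non-responders and as severe/extreme at later visits. Leave other missing values out, and list unrelated ENT procedures separately. State in advance that a version D participant who had such a procedure and then declined the extension counts as a failure only through 24 months and is shown as a planned exit at 36 months.
3. **Comparison table.** For participants with and without 36-month data, tabulate baseline NOSE, 24-month NOSE and 24-month responder status, with the recorded reasons for declining.

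Optional: bounds over the FAS with missing counted as failure and as success, labelled as bounds, and a 24-month QoL comparison (the schedule of assessments has no QoL before treatment).

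The cost is SAP wording, a few tables and a less favourable supportive figure. NOSE scores and reasons for declining are already due to be collected. The documents do not say that the indication for a later procedure is recorded, so it may have to be classified from site records. For losses other than declining the extension, Protocol 19.0 mentions only notes of contact attempts, so category (c) may be hard to divide further.
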